4.5 DOSE ESCALATION STOPPING RULES

The Medical Monitor will apply the following rules to determine if it is safe to proceed to the next Dose Level, or if dose escalation should stop. Pre-specified rules for pausing or stopping the whole study are described in Section 8.5 and rules for individual patient withdrawal are described in Section 8.4.

Should one of three patients in a Dose Level experience dose-limiting toxicity (DLT, see Section 8.1.2 for definition) within 7 days after receiving the first dose of the cells that is considered probably or definitely related to Descartes-30, 3 more patients will be enrolled and treated at that Dose Level. If only 1/6 of patients at that Dose Level has a DLT, and if the medical monitor agrees, treatment will proceed to the next higher Dose Level. If 2 or more out of 3 to 6 patients develop a DLT, no further patients will be dosed at that dose level. The MTD will be defined as the highest dose at which a maximum of 1 of 6 patients has a DLT. In Arm 2, up to 12 more patients who meet the eligibility criteria may be treated in each cohort (ARDS and PNA) at a dose up to MTD, provided that the medical monitor approves the enrollment of each such patient based on ongoing review of the cumulative safety data.

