Patients diagnosed with ARDS or PNA will undergo screening during which informed consent will be obtained and eligibility assessed. Up to 7 or 14 days may elapse between confirmation of PNA or ARDS diagnosis respectively and administration of the first infusion of study product. Patients will be dosed once per day for 3 consecutive days (Day 0, 1, 2). In Arm 1 (Dose Escalation), patients were monitored for 7 days after the first Descartes-30 infusion (unless they are discharged from the administering unit prior to Day 7) with a safety review on Day 7 (or last day in the administering unit, whichever comes earlier) to determine whether the next patient in the trial can be dosed. In Arm 2 (Dose Expansion), patients will be enrolled consecutively to receive treatment on Day 0, 1, and 2 at a dose up to the MTD determined in Arm 1. For both Arms, there will be an optional visit on Days 14 and 21 and a mandatory visit on Day 28. Long-term follow-up will occur at Day 90 (in-person or telephone contact).

Study Intervention:

The study product will be manufactured from qualified allogeneic donors under GMP standards. After the product passes Quality Control, it will be shipped to the study site for storage. Patients will receive the first dose of Descartes-30 cells via intravenous administration within 14 days of diagnosis of ARDS or within 7 days of diagnosis of PNA. Patients will receive two more infusions over the following 2 days unless they meet the criteria for holding dose or discontinuing study treatment.

In the dose escalation arm (Arm 1), the following doses of Descartes-30 cells are planned:

- Dose Level 1: 100 million cells administered on Days 0, 1 and 2
- Dose Level 2: 300 million cells administered on Days 0, 1 and 2
- Dose Level 3: 600 million cells administered on Days 0, 1 and 2

- Dose Level 4: 1200 million cells administered on Days 0, 1 and 2

An additional 12 patients per cohort (ARDS or PNA) may be enrolled at a dose up to MTD.

Study Duration: 30 months

Participant Duration: 3 months

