4.4 DOSE ESCALATION RULES

A minimum of three patients will be dosed at each dose level. In the dose escalation arm, there will be a minimum of 7 days between each patient's first cell infusion. At the time a patient is diagnosed with ARDS, the clinic will contact the sponsor who, by default, will assign the patient to the next slot in the active dose level. Patients will receive three doses of Descartes-30 cells on Days 0,1 and 2. On Day 7 or last day in ICU, whichever comes earlier, the Principal Investigator will review the clinical data with the Medical Monitor and authorize the next patient's infusion if there is no safety concern. The selection of Day 7 for safety review is based upon preclinical data demonstrating that Dnase expression wanes over 7 days. Furthermore, the study will not proceed to the next dose level until: 1) at least 3 patients in the previous dose level have been observed through Primary Safety Review; 2) no study stopping rules have been triggered; and 3) the medical safety monitor has reviewed the cumulative safety data and concluded and documented that the next Dose Level may be initiated.

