8.5 STUDY PAUSING AND STOPPING RULES

Premature termination of the clinical trial may occur because of a regulatory authority decision, change in opinion of the IRB or Medical Monitor. Additionally, recruitment may be stopped for reasons of particularly low recruitment, protocol violations, or inadequate data recording. Specifically, study will be stopped if:

- Study Sponsor or a Regulatory Body decides for any reason that subject safety may be compromised by continuing the study.
- The Sponsor decides to discontinue the development of the intervention to be used in this study.

The study will be **paused if:**

- There is death that is reasonably attributed to study product before Day 4.
- Two subjects with Grade 3 or 4 adverse events to vital organs that are assessed as probably or definitely related to study product within the first 7 days after first infusion.

If the study is paused for the reasons above, the PI and members of the study team will meet in person or by teleconference within 24 hours of the event to have a thorough discussion of the event. Meeting minutes capturing the review of any ongoing investigations, including next steps in the management of the subject and any proposed changes to the protocol will be forwarded to the Medical Monitor. If all parties agree as to the event resolution, then the pause will be lifted. If the study is paused for manufacturing reasons, the Sponsor will make recommendations for process improvements to be implemented. Pending successful completion of a process validation run, the manufacturing pause will be lifted.

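### In Arm 1 a late second or third infusion does not move the safety windows that run from the first infusion; one full 96-hour delay leaves 24 hours after dose 3 instead of up to 5 days

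*Combined protocol and SAP*

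**What the plan says.** Three infusions are planned, on Days 0, 1 and 2 (Section 4.4, Table 1). The Arm 1 safety rules are timed as follows.

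- **Expansion trigger (4.5).** Three more patients are added if one of three should "experience dose-limiting toxicity (DLT, see Section 8.1.2 for definition) within 7 days after receiving the first dose of the cells", with probable or definite relation to the product.
- **Review (4.4, 6.4).** It takes place "On Day 7 or last day in ICU, whichever comes earlier". The Synopsis gives the anchor: "patients were monitored for 7 days after the first Descartes-30 infusion".
- **Stagger (4.4).** "In the dose escalation arm, there will be a minimum of 7 days between each" patient's first infusion and the next patient's.
- **Pause rules (8.5).** One needs two subjects with Grade 3 or 4 vital-organ events "assessed as probably or definitely related to study product within the first 7 days after first infusion". The other covers a death attributed to the product before Day 4.

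Section 7.1.2.1 allows an infusion to be delayed by up to 96 hours for instability, related toxicity, a holiday or investigator discretion. The patient leaves treatment only if a dose is delayed for longer. Neither that section nor Sections 4.4, 4.5, 6.4 or 8.5 says what a delay does to the windows.

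Two other rules state no window. Section 8.1.2 counts any related Grade 3-5 toxicity as a DLT, and Section 4.5 says "If 2 or more out of 3 to 6 patients develop a DLT, no further patients will be dosed at that dose level". The MTD definition in 4.5 also has no time limit.

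**The concern.** The windows fit a schedule in which all dosing ends on Day 2. When dose 2 or 3 is late, the time to observe the patient after the last dose shrinks by the length of the delay, while the next patient, or the next dose level, can still be released at Day 7. One permitted reason for delay is failure of the pre-infusion stability check, so a less stable patient may be the one observed for the shortest time.

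The rules also stop agreeing with each other. A late related Grade 3-5 event is a DLT by definition and, on the wording, counts in the two-or-more and MTD rules. After Day 7 it does not count in the one-of-three trigger. A level with one such event need not be expanded to six before escalation, and the next level's per-infusion dose is two or three times higher (Table 1). Arm 2 is then dosed "at a dose up to the MTD determined in Arm 1".

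**Working it through.** **Inputs.** Planned infusions at 0, 24 and 48 h (4.4). Delay of up to 96 h (7.1.2.1). Minimum gap between infusions 12 h (6.2). Window end at 7 days = 168 h from first infusion (4.5, 8.5; Day 7 in 4.4 and 6.4). Mandatory Arm 1 labs daily on Days 3-6 and on Day 7 while the patient is in the unit (6.3, 6.4). The plan states no figure for the time left after dose 3, so the on-schedule case is the baseline.

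**Time left after dose 3.** Let D be the total delay to dose 3 in hours, with doses otherwise 24 h apart. Dose 3 is at 48 + D, and the time left is 168 − (48 + D).

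| D (h) | Dose 3 | Time left | Mandatory lab sets after dose 3, to Day 7 |
|---|---|---|---|
| 0 | 48 h, Day 2 | 120 h (5 days) | 5 (Days 3-7) |
| 24 | 72 h, Day 3 | 96 h | 4 |
| 48 | 96 h, Day 4 | 72 h | 3 |
| 96 | 144 h, Day 6 | 24 h | 1 (Day 7) |
| 192 | 240 h, Day 10 | −72 h | 0 |

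The last row is two full delays. It is possible only if the 96 hours applies per dose, and it is a remote case. The window is used up when D = 168 − 48 = 120 h. If a dose 2 delayed by 96 h (at 24 + 96 = 120 h) is followed by dose 3 at the 12-hour minimum, dose 3 is at 132 h and 168 − 132 = 36 h remain.

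**Delay of dose 1.** The 7-day windows start at the actual first infusion, so a delay of dose 1 moves them all and costs nothing.

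**Which events are exposed.** After one full delay, the 4-hour DLT criteria of 8.1.2 apply shortly after 144 h, inside 168 h, so they remain covered. Later related toxicities do not. Take a related Grade 4 event 2 days after dose 3. On schedule it falls on Day 2 + 2 = Day 4 and meets the trigger. After one full delay it falls on Day 6 + 2 = Day 8: a DLT under 8.1.2, but outside the 4.5 trigger and the 8.5 vital-organ window.

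**Death pause rule.** On schedule it runs 4 − 2 = 2 days beyond dose 3. With dose 3 on Day 6 it lapsed 6 − 4 = 2 days before that dose.

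**Opening the next level.** First infusions are at least 7 days apart, so at patient 3's Day 7, patients 1, 2 and 3 are at least at Days 21, 14 and 7. Days observed after dose 3, for a patient with the delay shown:

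- No delay: 21 − 2, 14 − 2, 7 − 2 = 19, 12, 5.
- One full delay: 21 − 6, 14 − 6, 7 − 6 = 15, 8, 1.
- Two full delays: 21 − 10, 14 − 10, 7 − 10 = 11, 4, −3.

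After one full delay only the cohort's last patient falls below 5 days at this gate. Release of the next individual patient is affected whichever patient is delayed.

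**The case against.** The strongest reply is that clinical judgment covers the gap.

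- Every Arm 1 infusion is followed by 4 hours of observation (7.1.2.3), and toxicities are expected within several hours (7.2.2).
- Arm 1 labs are mandatory on each infusion day, whenever it falls (6.2).
- The 7-day stagger is a minimum. The investigator and medical monitor release each next patient only if there is no safety concern. A new level also waits until "the medical safety monitor has reviewed the cumulative safety data and concluded and documented that the next Dose Level may be initiated".
- Arm 1 adverse events are recorded to Day 90. SAEs are reported to 7 days after the last infusion, and related SAEs beyond that (8.2.1).
- The medical monitor must approve each Arm 2 patient (4.5), and the sponsor can stop the study on safety grounds at any time (8.5).
- A delay for related Grade 3 or higher toxicity would usually follow an event already counted as a DLT. The gap is therefore mainly about delays for instability, holidays or discretion.

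All of this stands and lowers the risk. It does not replace a pre-specified trigger: discretion allows expansion after a late DLT, but the rule as written does not require it.

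The 5-day baseline is also a maximum. An on-schedule patient who leaves the ICU on Day 3 is reviewed about 1 day after dose 3. For that patient, however, the DLT window and the stagger still run to Day 7; after a late dose 3 they do not extend.

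A reader might infer that late DLTs are lost altogether, or that the MTD must come out wrong. The documents do not support that. The two-or-more and MTD rules carry no window, so a late DLT can still count there, and related SAEs remain reportable. Nor do they support reading every delayed infusion as a problem, since dose 1 is unaffected.

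**Conclusion.** The point holds for Arm 1 patients whose dose 2 or 3 is late. No text moves the expansion window, the Day 7 review, the stagger or the two pause windows. One full 96-hour delay leaves 24 hours after dose 3 (36 hours at the minimum gap) against up to 120 on schedule. Two full delays would put dose 3 on Day 10, after the window has closed. This assumes that the limit is per dose, which the wording of 7.1.2.1 suggests but does not state outright. The exposed events after one full delay are related Grade 3-5 toxicities arising after Day 7.

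The figures assume doses 24 hours apart apart from the stated delays, and a patient still in the ICU at Day 7. The documents give no frequency of delays, so how often this would matter cannot be estimated. Severity is minor to should-fix: a gap in the rules with discretionary cover, and cheap to close. The Synopsis describes Arm 1 monitoring in the past tense while 4.4 and 4.5 use the future. If Arm 1 is complete, the point becomes a check on events already recorded.

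**What to change.** For Arm 1 patients whose dose 2 or 3 is given after its planned day, and only for them:

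1. End the DLT window and the 8.5 vital-organ window, and hold the primary safety review, at the later of Day 7 and 5 days after the last infusion given. Release no next patient or level before then.
2. Use that same window in the expansion, two-or-more and MTD rules of 4.5.
3. Continue the 6.3 daily labs to that point while the patient is in the unit. Otherwise, do one adverse-event check before the review.
4. Run the death pause rule to the later of Day 4 and 2 days after the last infusion (Day 8 after one full delay).
5. Confirm in 7.1.2.1 that 96 hours is per dose.

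**Cost.** Amendment wording, plus a wait equal to the delay of the last dose. After one full delay the review is at 144 + 120 = 264 h, Day 11: 4 days later, with up to 4 extra lab sets (Days 8-11). After two, it is at 240 + 120 = 360 h, Day 15: 8 days later, with up to 8 sets. On-schedule patients keep the current rule, including review at early ICU discharge.

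Five days is chosen because it is the most that the planned schedule gives. Section 4.4 justifies Day 7 by DNase expression waning over 7 days, but 7 days after dose 3 would move every on-schedule review to Day 9, so it is not proposed.

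If Arm 1 is complete, list the actual infusion days and reclassify related Grade 3-5 events by this window before confirming the Arm 2 dose. The cost is then one listing and one reclassification.

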SEM	Standard Error of the Mean
SM	Starting Materials
SOFA	Sequential Organ Failure Assessment
SUSAR	Serious Unexpected Adverse Reaction
TK	Toxicokinetic(s)
WHO	World Health Organization

PROTOCOL SYNOPSIS

Title: Phase I/IIa Study of Descartes-30 in Acute Respiratory Distress Syndrome.
Study Description: This is a Phase I/IIa, open-label, emergency study to test the safety of Descartes-30 cells in patients with acute respiratory distress syndrome (ARDS) and severe pneumonia (PNA). The cell product consists of Mesenchymal Stem Cells (MSCs) engineered to express DNase1 and DNase1L3 to degrade Neutrophil Extracellular Traps (NETs), which are a cardinal and causative feature of ARDS. In the dose escalation arm (Arm 1), the study will enroll three patients with ARDS into each of four successive dose levels to test escalating doses of Descartes-30. An additional 12 patients with ARDS (ARDS Cohort) and 12 patients with severe pneumonia (PNA Cohort) will be enrolled into a dose expansion arm (Arm 2).
Objectives: **The primary objective** is to assess the safety of Descartes-30 in patients with moderate-to-severe ARDS. Safety will be determined principally by assessment of adverse events (AEs) and serious adverse events (SAEs).
[REDACTED]

The exploratory objectives are:
[REDACTED]

Endpoints: The primary endpoint is the Maximum Tolerated Dose (MTD) defined as the highest Dose Level at which no more than one patient has shown Dose-Limiting Toxicity (DLT).
[REDACTED]

Study Population:

The study will enroll about 36 patients: about 12 patients in a dose escalation arm and about 24 patients in an expansion arm. The major eligibility criteria are as follows: (1) 18 years or older; (2) respiratory failure; (3) ARDS diagnosis per Berlin criteria within 14 days of first cell infusion OR severe PNA per ATS/IATS criteria within 7 days of first cell infusion; (4) maximal medical therapy already in place, in the opinion of the treating physician; (5) informed consent from participant or health care proxy. Patients will be excluded if they (1) are moribund with expected survival <24 hours, (2) are pregnant (3) have severe baseline morbidity prior to diagnosis of ARDS or PNA, (4) have used Pulmozyme® (dornase alfa) after diagnosis of ARDS or PNA. For complete list of inclusion and exclusion criteria, see Full Protocol.

Phase:

I/IIa

Study Site:

Multi-center

Study Design:

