4.2 OVERALL STUDY DESIGN

This is an open-label, multi-center, Phase I/IIa study to evaluate the safety and tolerability of Descartes-30, allogeneic Mesenchymal Stem Cells (MSCs) modified to secrete recombinant human Dnase1 and recombinant human Dnase1L3 in patients with ARDS and PNA. The study will enroll about 33 patients: about 12 patients in a dose escalation arm (Arm 1) and about 12 patients in each cohort (ARDS and PNA) of an expansion arm (Arm 2). The study will involve four planned Dose Levels. An expansion arm (Arm 2) will dose up to 24 additional patients with a dose deemed to be safe in Arm 1 for additional characterization of Descartes-30 risk/benefit in ARDS and PNA. Patients in the dose escalation arm (Arm 1) will be enrolled in staggered fashion to allow adequate safety monitoring period in between patients.

For both arms, patients who are diagnosed with ARDS of any severity as per Berlin Criteria⁵ ([Appendix C](#)) will be screened and enrolled into the next available slot in the ARDS Cohort. In Arm 2, patients with radiographically confirmed PNA requiring inpatient hospitalization will be screened and enrolled into the PNA Cohort. The total dose will be split into three days and the first dose should be given within 14 days of ARDS diagnosis. Safety is monitored daily for up to 7 days while patient is in the administering unit (ICU or IMC for ARDS Cohort, ICU, IMC, or acute care floor for PNA Cohort), with a primary safety review on Day 7 or last day of stay in administering unit, whichever comes earlier. After Day 7, patients will be assessed on Day 14, 21 and 28 if they are still in the administering unit for a follow-up visit. There will be one more contact on Day 90 for long-term follow-up. This visit can be in-person or via telemedicine.

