9.2 SAFETY

The following safety parameters will be tabulated and analyzed descriptively: adverse events, clinical laboratory tests, ECGs, physical examinations, and vital signs. Dose escalation rule determination of MTD is described in Section 4.4.

[figure not shown]

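### The MTD definition does not require a higher dose to have failed, so a cleared Level 4 is reported as the Maximum Tolerated Dose when no intolerable dose was found

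*Combined protocol and SAP*

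**What the plan says.** The synopsis (Endpoints) makes the MTD the primary endpoint and defines it as "the highest Dose Level at which no more than one patient has shown Dose-Limiting Toxicity (DLT"). It gives no denominator. Section 4.5 words it differently: "The MTD will be defined as the highest dose at which a maximum of 1 of 6 patients has a DLT".

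The escalation rule is a standard 3+3. Section 4.4 sets a minimum of three patients per level. Under Section 4.5, one DLT in three patients adds three more at that level, and one in six allows escalation if the medical monitor agrees. The failure rule is: "If 2 or more out of 3 to 6 patients develop a DLT, no further patients will be dosed at that dose level". Section 4.2 plans four levels, and Table 1 ends at Level 4, 1200 million cells on each of three days. For Arm 1 the synopsis says that "the study will enroll three patients with ARDS into each of four successive dose levels".

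The MTD then sets a ceiling. The synopsis (Study Design) has Arm 2 treated "at a dose up to the MTD determined in Arm 1", and Section 4.2 says that Arm 2 "will dose up to 24 additional patients with a dose deemed to be safe in Arm 1". Section 4.5 allows Arm 2 dosing "provided that the medical monitor approves the enrollment of each such patient based on ongoing review of the cumulative safety data".

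No readable text says what is reported if no level fails. Section 9.2 adds no rule of its own: "Dose escalation rule determination of MTD is described in Section 4.4".

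**The concern.** A maximum tolerated dose is normally understood as a limit that the trial has located: this level was acceptable and the next was not. The definition here asks only for the first half. When escalation runs out of planned levels before it meets a failing one, the definition is still satisfied, by the top level.

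That outcome is close to the planned case. Twelve patients over four levels means that no level was expanded. Levels 1 to 3 must then each have cleared on 0/3, and Level 4 either cleared on 0/3 or stopped on two or three DLTs. Section 4.3 also says that the secreted enzymes are not expected to have significant toxic effects. The course that the sponsor appears to expect is therefore one in which no level fails.

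At stake is the meaning of the primary result. A report that the MTD is 1200 million cells would tell a later trial's designers that a toxicity limit had been found there. The data would support only the statement that this was the highest dose planned and that it was not stopped.

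**Working it through.** **Planned size.** 4 levels × 3 patients = 12 in Arm 1, and 12 + 24 in Arm 2 = 36. Both match the synopsis.

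**Inputs.** The escalation rules come from Sections 4.4 and 4.5. The documents give no DLT rate, so every rate below is an assumption. DLTs are taken as independent, and the medical monitor is taken to agree to each permitted escalation.

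**Per level, with true DLT rate p:**
- cleared on 0/3: a = (1−p)³
- cleared on 1/6: b = 3p(1−p)² × (1−p)³ = 3p(1−p)⁵
- cleared: c = a + b

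| p | a | b | c |
|---|---|---|---|
| 5% | 0.857 | 0.116 | 0.973 |
| 10% | 0.729 | 0.177 | 0.906 |
| 15% | 0.614 | 0.200 | 0.814 |
| 20% | 0.512 | 0.197 | 0.709 |

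**Whole trial:**
- no level fails, so Level 4 is named the MTD: c₁c₂c₃c₄
- the same, with Level 4 resting on 0/3: c₁c₂c₃a₄
- Level 1 fails, so no dose qualifies: 1 − c₁
- MTD lies below a level that failed: 1 − c₁c₂c₃c₄ − (1 − c₁)

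For a flat 10%: 0.906⁴ = 0.674; 0.906³ × 0.729 = 0.542; 1 − 0.906 = 0.094; 1 − 0.674 − 0.094 = 0.232.

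| Assumed rates, Levels 1–4 | Level 4 named MTD, no level failed | of which on 0/3 | MTD below a failed level | Level 1 fails |
|---|---|---|---|---|
| 5% flat | 90% | 79% | 7.5% | 2.7% |
| 10% flat | 67% | 54% | 23% | 9.4% |
| 20% flat | 25% | 18% | 46% | 29% |
| 5, 10, 15, 20% | 51% | 37% | 46% | 2.7% |

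The column headed 'of which on 0/3' is also a percentage of all trials. A simulation of 400,000 trials agreed with the no-level-fails, Level-4-on-0/3 and Level-1-fails probabilities to within 0.001.

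**Other rising curves.** With 2, 5, 8 and 10%, Level 4 is named the MTD in 82% of trials (66% on 0/3). With 5, 10, 20 and 33%, it is 27% (19% on 0/3).

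**Reading of the two definitions.** Taking the 1-of-6 wording in Section 4.5 as a ceiling reconciles it with the synopsis and lets a level cleared on 0/3 qualify. Taking it to require six patients would leave a trial without any DLT with no MTD at all, because no rule enrols patients four to six after 0/3. Neither reading gives a reportable result for the case where the top level clears without a DLT and no limit was found.

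**The case against.** The strongest reply is that the protocol defines its own term. A Level 4 that clears meets the stated definition, so reporting it as the MTD is correct as pre-specified. Section 9.1 says that the objectives are not inferential, and whether to write 'MTD' or 'MTD not reached' is partly convention. This stands to the extent that no analyst would be breaking the plan. It does not answer the point, because a descriptive endpoint should still describe what was observed, and the label implies a limit that was not observed.

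The largest percentages also arise where the assumed DLT rate is lowest, which is where the top dose is in fact tolerable and the label does least harm. That is fair. The percentages measure how often the label lacks a failed level above it, not how often a toxic dose is endorsed.

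A reader might infer four stronger things, none of which the documents support.
- *Arm 2 patients would be dosed unsafely.* Arm 2 is limited to a dose judged safe in Arm 1, with the medical monitor approving each patient.
- *The endpoint hides a weakness in the evidence from three patients.* The exact 95% interval for 0/3 does run from 0 to 71%. A Level 4 with an assumed true rate of 33% would clear in 43% of trials that reach it (31% at 40%). These are properties of 3+3 escalation, and no rewording of the MTD alters them.
- *An unexpanded 1/3 could become the MTD.* The synopsis alone would allow it, but Section 4.5 requires three more patients after 1/3.
- *Arm 2 could open after a Level 1 failure.* Section 4.5 stops dosing at that level, and no dose would then have been found safe, so Arm 2 has no permitted dose. Only an explicit sentence is missing.

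**Conclusion.** The point holds as a matter of what the primary endpoint reports. If no level has two or more DLTs, the stated rule names Level 4 as the Maximum Tolerated Dose, possibly on 0/3, although no intolerable dose was found. Under assumed flat DLT rates of 5%, 10% and 20% this occurs in about 90%, 67% and 25% of trials, and in 51% under rates rising from 5 to 20%. These figures rest on assumed rates, independence and the monitor's agreement at each step; a refusal would make Level 4 less likely to be reached. When a level above Level 1 does fail, the definition works in the conventional way.

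The consequence is a misleading primary conclusion. It is not a change in who is dosed or how much they receive, and it does not call for more patients per level. It is worth correcting because the endpoint is primary and the correction is small.

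**What to change.** Put one definition in both the synopsis and Section 4.5, for example:

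> The MTD is the highest dose level cleared under the escalation rule (0/3, or at most 1/6 after expansion) below a level at which 2 or more patients had a DLT. If no level has 2 or more DLTs, report MTD not reached, name the highest cleared dose level with its number treated and DLT count, and cap Arm 2 at that level.

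This still accepts a level cleared on 0/3, which is why the counts should be reported beside it. It adds no patients and leaves the escalation rules and the Arm 2 ceiling as they are.

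The cost is a less definite headline: the primary result may read 'MTD not reached'. Timing also matters. The synopsis describes Arm 1 monitoring in the past tense, which suggests but does not prove that Arm 1 had already been run. If it had, the change should be dated and reported as a clarification made after the escalation data.

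Two optional clarifications could go in at the same time: a sentence that no MTD is declared and Arm 2 does not open if Level 1 has two or more DLTs, and a correction of the Section 9.2 cross-reference from 4.4 to 4.5.
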